## **1. Abstract**

This research protocol describes a randomized control trial to compare two different methods of managing home oxygen therapy in premature infants. This is a multicenter study involving 9 centers. We plan to enroll a total of 196 infants, of which 68 will be from Boston Children's Hospital (BCH). The current standard for oxygen management includes brief assessments of a patient's oxygen saturation status during monthly clinic visits. The patient's oxygen status between visits is assumed to be acceptable; although it is possible for significant hyperoxia or hypoxia to occur, providers have no data to help with decision-making. In many centers, final steps before discontinuing home oxygen therapy (HOT) often include polysomnography (PSG), which can be costly and requires the inconvenience of rehospitalization. Advances in data storage and pulse oximetry technology have expanded potential uses for recorded home oximetry (RHO) in the accurate assessment of hypoxemia. At Boston Children's Hospital, we have pioneered the use of recorded home oximetry (RHO) in other research protocols, and shown that it can be a simple and convenient method for parents to transmit oximetry data to providers.

In this trial, we will randomize premature infants who require HOT at time of discharge from the NICU, who are referred for follow-up at the Center for Healthy Infant Lung Development. At the time of their first outpatient appointment, infants will be randomized to one of two treatment arms:

**Arm A (“Standard therapy”):** Infants' oxygen will be increased, decreased, or maintained based on brief structured assessments during monthly clinic visits. Polysomnograms will be utilized prior to final discontinuation of oxygen. RHO will only be utilized on the night prior to and during the polysomnogram to compare these two modalities.

**Arm B (RHO):** Infants will have the same monthly clinic assessments as in Arm A, but also will utilize RHO to potentially increase, decrease or maintain oxygen between monthly visits. Parents will transmit a minimum of 25 hours (1500 minutes) of stored RHO data (approximately 4 days, 8 hours per day) every 4-7 days. Changes in oxygen needs will be made based on standardized objective criteria. To determine discontinuation of oxygen, RHO will be utilized instead of polysomnography.

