**- Baseline Visit ( First Initial Visit): V0**  
**(For all patients in ARM A and ARM B )**

After confirming eligibility and obtaining the consent form, growth parameters, nutrition notes, NICU discharge summary, demographics and PedsQL survey will be obtained at this visit.

Medical records will be transferred to UMass using methods to ensure data safety, for abstraction by study staff. [name] will train study staff in abstraction of medical records.

Each site PIs will perform the baseline growth assessment and perform randomization at time of enrollment. We will perform block randomization to ensure equal distribution within each site.

Study staff at BCH will ask parents to complete a PedsQL at the initial (baseline) clinic visit. Research staff at BCH will hand the questionnaire to the parent for self-report in order to minimize response bias and standardize methods. If for some reason the PedsQL is not completed in clinic, staff at BCH or UMass will contact the family to complete the survey over the phone shortly after the visit. Growth and nutrition information from this visit will also be recorded.

At the end of the visit, contact information will be confirmed, and the parent will be reminded about the next planned phone/clinic visit and interview.

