**d. Statistical Power and Sample Considerations**

*Analyses for Aim 1:*

Aim 1: To evaluate the effects of a data-driven HOT management protocol on parent(s) quality of life.	Hypothesis 1.1: Parents of patients weaned from HOT using a data-driven management protocol will have improved quality of life compared to their status at time of NICU discharge compared to patients weaned using the current standard HOT management protocol.
--	--

For the impact of oxygen management protocol on the family's emotional health, we will use the PedsQL. We are performing these scales at the beginning of the outpatient HOT management process, to establish a baseline, and then will repeat these measures at the end of the HOT weaning process (6 months after discontinuation of HOT). We will test the association of oxygen management protocol with change in each measure using the Student's *t*-test to analyze the difference between intervention groups. Multivariate linear regression models will adjust for potential confounding variables, including parent and medical attributes.

Power calculation for hypothesis 1.1:

Power calculations are based on the primary analyses (t-test). A sample size of 130 will give 80% power, with 0.05 two-sided type I error rate, to detect a 20% absolute difference in emotional role limitation on the PedsQL, which we consider to be clinically significant.

*Analyses for Aim 2:*

Aim 2: To evaluate the impact of a data-driven HOT management protocol on duration of HOT.	Hypothesis 2.1: A data-driven HOT protocol will shorten duration of HOT therapy compared to the current standard HOT management protocol.
---	--

For the primary outcome, duration of HOT, the interval from date of first outpatient clinic visit/enrollment to discontinuation of HOT will be determined. Mean duration of HOT between the two groups will be compared.

Based on our experience weaning over 130 premature infants from O2, we expect the mean duration of HOT in our standard treatment group (clinic-based weaning) to be 144+/-66 days, and we anticipate that RHO weaning strategies will decrease the median duration by 25% (36 days) to 108 days. A total sample of 98 infants per group provides 97% power to detect this effect of the RHO strategy (two-tailed, alpha=0.05, see Table 2).

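### The baseline PedsQL is not required to precede randomization, and at BCH a missed one may be phoned in afterwards, so knowledge of the arm could bias the change-from-baseline primary outcome

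*Combined protocol and SAP*

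**What the plan says.** The Abstract sets the time of allocation: "At the time of their first outpatient appointment, infants will be randomized to one of two treatment arms". The baseline-visit text in section 4f agrees: "Each site PIs will perform the baseline growth assessment and perform randomization at time of enrollment". Section 4f also places the baseline PedsQL at this visit, and gives the reason for using a self-completed form: "Research staff at BCH will hand the questionnaire to the parent for self-report in order to minimize response bias and standardize methods". If the form is not completed in clinic, staff at BCH or the coordinating center are to "contact the family to complete the survey over the phone shortly after the visit". No time window is attached to that call.

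No section says that the PedsQL must be finished before the allocation is made or disclosed.

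Section 4e lists parent quality of life as primary measure (b), defined relative to baseline. Section 5d, under Aim 1, describes the baseline's purpose: "We are performing these scales at the beginning of the outpatient HOT management process, to establish a baseline". It then compares the change between arms with a t-test, supported by regression adjusting for parent and medical attributes. Neither section mentions the timing or mode of the baseline PedsQL.

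**The concern.** A baseline that is subtracted from the outcome should be fixed before anyone knows the allocation. Here the parent is both the respondent and a person who cannot be blinded: under Study Procedures in section 4f, Arm B families receive a study oximeter, a recorder and instruction. A baseline completed after that point may reflect the parent's reaction to the arm as well as the family's state at entry.

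The reaction concerns what the instrument is meant to measure, since the Abstract hypothesizes that home recording reduces emotional and financial stress. A reaction that differs by arm would shift the baselines and enter the treatment comparison with its sign reversed. A true pre-allocation value cannot be recovered afterwards.

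The phone fallback is where this is certain to happen, because the call comes after the visit at which randomization took place. The gap is wider than the fallback, however. A form completed in clinic but after allocation has the same weakness, and the text allows that too.

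**Working it through.** **1. Order of events.** The Abstract and section 4f put randomization at V0. Section 4f puts the PedsQL at V0 in no stated order, with a phone fallback after V0. A phoned baseline is therefore post-randomization, and an in-clinic baseline may be before or after. The documents do not state when the parent learns the arm. I infer that it is at or soon after V0, from randomization at that visit and the equipment and instruction given to Arm B.

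**2. The plan's own figure.** Section 5d gives 130 for 80% power at two-sided 0.05 and a 20% absolute difference, read here as 20 points on the 0 to 100 scale. No SD is given, so 130 cannot be reproduced directly. Solving for the SD:

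- 130 in total (65 per arm): SD = 20 / [(1.960 + 0.842) × √(2/65)] ≈ 40.7.
- 130 per arm: SD = 20 / [(1.960 + 0.842) × √(2/130)] ≈ 57.6.

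This point disputes neither number. The SD of 40.7 is used only to scale the bias, with an assumed SD of 20 as a contrast.

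**3. Bias formula.** Let f_A and f_B be the shares of baselines taken after allocation, and s_A and s_B the mean shifts that knowing the arm causes in them. Compared with a clean baseline, the difference in mean change (B minus A) is off by −(f_B·s_B − f_A·s_A). With a common share f, and s = s_B − s_A, the size is f × s.

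- Higher scores mean better functioning. If Arm B parents feel relief, their baseline rises, their gain shrinks and the bias works against RHO.
- If Arm B parents feel added burden, the bias favours RHO.

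**4. Size.** The documents give neither f nor s, so both are assumed. Section 5d enrolls 98 per group, and Table 2 assumes 85% completion: 0.85 × 98 ≈ 83 per arm. The standard error is SD × √(2/83), which is 6.3 at SD 40.7 and 3.1 at SD 20. The last two columns give the two-sided rejection probability with no true effect (nominal 5%).

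| Share late f | Shift s | Bias f × s | SD 40.7 | SD 20 |
|---|---|---|---|---|
| 10% | 5 | 0.5 | 5.1% | 5.3% |
| 25% | 10 | 2.5 | 6.8% | 12.7% |
| 50% | 10 | 5.0 | 12.4% | 36.4% |

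**5. If only BCH has late baselines.** BCH plans 68 of 196 infants, 68/196 = 0.347. Reading f as the late share within BCH and zero elsewhere, the biases become 0.347 × 0.5 = 0.17, 0.347 × 2.5 = 0.87 and 0.347 × 5 = 1.7 points. For the largest of these, the error rate is about 5.9% at SD 40.7 and just under 9% at SD 20.

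**6. Mode of completion.** If a phone interview shifts scores by m regardless of arm, its contribution is m × (f_B − f_A) in size. That is zero when the phoned share is the same in both arms.

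**The case against.** The strongest reply is that this is a contingency. The form is planned for the clinic and the phone call is for exceptions. If exceptions are few, the table's first row applies and the error rate hardly moves. This stands, and it is why the conclusion is conditional. Still, exceptions are foreseeable: the monthly-visit text in section 4f names time constraints as a reason the PedsQL may be missed, and V0 also carries consent, eligibility, growth assessment and randomization.

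A second reply is that parents know their arm at follow-up too, so a lasting reaction would appear in both scores and partly cancel. That is right if the target is an effect free of parental awareness. It does not help if the target is change from the family's state before allocation, which is how section 5d uses the baseline.

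Third, the fallback text is written for BCH. That also stands. Other sites' arrangements are not described, so it should not be assumed that every site phones late baselines, nor that none does.

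A reader might also infer that moving from self-report to a phone call is itself a source of between-arm bias. The documents do not support that. Section 4f allows phone completion at the monthly and 3-month post-wean time points as well, in both arms. Nothing suggests that its use differs by arm, so mode alone adds noise.

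**Conclusion.** The gap is real and worth closing. As written, the plan permits a baseline taken after allocation, parents cannot be blinded, the baseline enters a primary change outcome, and no rule covers late values. Such baselines could bias that outcome.

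A reader might infer that the change score is biased, or that the bias favours RHO. The documents support neither. They do not give the number of late baselines, the size of any reaction or its direction, and the moment at which the parent learns the arm is inferred. On the assumptions above, the effect runs from negligible (0.5 points) to material (5 points, with half of the baselines late and a 10-point difference in reaction). It is about a third of that if late baselines occur only at BCH. Even the upper end is well below the target read as 20 points, so the main cost would be to the error rate and to the credibility of the baseline. The remedy is cheap, which is the reason to make the change.

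**What to change.** In section 4f, for all sites: require the baseline PedsQL to be completed at V0 before the allocation is released, and record its date, time and mode.

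In section 5: flag any baseline still obtained after allocation, and pre-specify a sensitivity analysis of the Aim 1 t-test and regression that either excludes those baselines or compares post-wean scores alone. The two options differ. Excluding late baselines drops those families from the change analysis, and lateness arising after allocation may itself depend on the arm. Comparing post-wean scores keeps every family with a follow-up score and relies on randomization for baseline balance, possibly with some loss of precision. Adding a contaminated baseline as a covariate would not remove the problem.

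The cost is a few sentences of text, a few recorded fields, and sometimes a short wait at V0 while the parent finishes the form. Randomization should stay within V0 and not wait for a later phone call, because the HOT-duration clock in section 4e starts at the first outpatient appointment and a delay would affect the other primary outcome.

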**- Monthly Visits: ( ARM A and ARM B): (V1 onwards until wean)**

1. Parents will be asked to complete the PedsQL at follow-up monthly clinic visits until the infant is weaned. In case the PedsQL is not obtained during the clinic visit, due to time constraints, these surveys can be conducted over the phone in the privacy of their home. This is to ensure we have consistent data on all patients in our study.
2. Growth parameters (WHO) and nutrition notes will be obtained at all monthly visits (prior to weaning).

**- Post Wean Follow- Up visits:**

The Post-Wean follow- up (f/u) visits are at 1 month, 3 month and 6 month after the patient has been weaned off oxygen.

- 1 month post-wean f/u visit: At the 1 month post wean visit, growth parameters, nutrition notes and will be collected. For ARM B patients only, a **post study Home Oximetry Feasibility Questionnaire** will be given to parents to complete. This questionnaire would be conducted at the 1 month post-wean visit, however, if unable to obtain at this time point, due to missed visit or lost to follow-up it can be collected post-wean at any time at a clinic visit or over the phone.
- 3 Month post-wean f/u visit: At the 3 month post-wean visit, a **PedsQL will be obtained. If unable to complete at this time, study staff at BCH or UMass will contact to obtain the survey over the phone.**
- 6 month post-wean f/u visit (Final Visit): At the 6 month post-wean visit, growth parameters and nutrition notes will be collected. In addition, the provider will inquire about respiratory-related hospitalizations or emergency department visits that may have occurred since oxygen discontinuation. Medical records will be reviewed to confirm this data. This visit marks the completion of participation in the study

Study staff will complete a final disposition form for every subject as a way to declare them officially off of the study.

**- All Visits:**

**Adverse events:**

Rehospitalizations and emergency department visits will be determined through parent interview/phone calls during and in between the monthly clinic visits as well as during the post weaning period: (1 month, 3 month and 6 months after oxygen discontinuation), and will be verified through medical record review/parent/site communication. This will be recorded on the Adverse Event form.

**- ARM B only:**

Oximetry data for infants in Arm B will be transmitted by mail or email to study staff every 4-7 days, and after analysis will be transferred to structured data collection forms. For patients who do not have internet access, or who do not feel comfortable using a computer, pre-stamped envelopes with blank data cards will be provided. The data cards will be labeled with the patient's coded deidentifier so that no identifying patient information is on the card or envelope. The participants will simply mail their data card every 4-7 days. All participants will mail the data card to UMass Medical Center, which will serve as the central data coordinating center

**- ARM A Only:**

Polysomnogram data for infants in Arm A will also be extracted into data collection forms after completion of the polysomnogram.

**Follow-up with sites:** Every month, study staff, led by [name], will conduct a conference call with all site PIs to review recruitment progress and confirm status of currently enrolled patients. Notification of infants who have successfully discontinued HOT will be verified.

**Removal of subjects from the study:** If it is required to permanently discontinue the study intervention because of adverse effects the participant will be withdrawn from the study. The Investigator may also remove a subject from the trial if he or she feels this action is in the best interest of the subject. Parents can withdraw their children from the study at any time for any reason.

### **Study Procedures:**

- **PedsQL:**

The PedsQL consists of 36 items that assess eight health domains labeled physical functioning, role limitations due to physical or emotional health, bodily pain, general health, vitality, social functioning and mental health. For the purpose of reporting results, the raw scores rating each health domain are transformed to a score that can range from 0 to 100, with higher scores reflecting better functioning. Considerable information about the validity and reliability of this measure is available. We have performed a preliminary review of the PedsQL with our Parent Advisory Board, and will work with them to augment these measures and ensure that planned measures adequately address the parent perspective.

- **Oxygen Management Protocols**

At time of enrollment, infants will be randomized to one of the oxygen management protocols (utilization of RHO or routine care). Infants randomized to utilization of RHO will receive a Masimo Rad-8 pulse oximeter and serial data recorder to record HbO2 SAT and heart rate, and will receive instruction regarding when to record the infant and how to send in data.

- **Home Pulse Oximeter Recording Procedures**

The recording system we used for prior studies and plan to use for this study is the Masimo Rad-8 pulse oximeter with an attached data recorder and removable memory card with ample capacity (2 GB) to store the continuous data recorded for each infant. The oximeter will be set for the minimum (2 sec) averaging time. Since the study oximeter will not be used as a monitor but rather as a (**continuous**) recorder, it will be preset in the sleep lab mode; there will be alerts for “probe off” and “low battery,” but no alarms for HbO2 SAT or heart rate, and no visual displays of HbO2 SAT. ***Infants will utilize their clinically-provided monitor as determined by their primary clinical team to serve as their monitor.***

During the 4-7 day evaluation periods to determine readiness to wean or status post wean, parents will be instructed to use the oximeter continuously during nocturnal sleep periods for a minimum of 25 hours (1500 mins/approximately 8 hours per day for 4 days). At the end of the 4-7 day period, data will be downloaded and electronically sent via secure email. For families who do not have access to a computer, and/or are uncomfortable with technology we will provide with data cards that can then be sent via provided protected express shipping envelopes with postage. All data cards will be sent to [name] at UMass for analysis as soon as they are removed from the oximeter.

Over the 4-7 days, a minimum of 25 hours (1500 minutes) of data is to be sent to UMass and deemed interpretable before any change in supplemental oxygen management is made. If the data is deemed inadequate or unreadable, the parent will be notified and no change in oxygen management will be made. Infants randomized to routine care will be weaned at monthly outpatient clinic visits per structured clinic-based protocol. Weaning parameters for each arm are listed in Table 1.

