#### **4.e. Definition of Primary and Secondary Outcomes/Endpoints**

Primary measures: (a) Total duration of home oxygen therapy (HOT) from the first outpatient pulmonary appointment to discontinuation of supplemental O2; and (b) Parent quality of life, assessed by differences in the post-weaning PedsQL baseline.

Secondary measures: (a) Number of rehospitalizations and emergency department visits from 1st clinic visit through 6 months after discontinuation of HOT; (b) Change in weight and weight-for-length z-score from 1st clinic visit to 6 months after discontinuation of HOT; and (c) For patients who will receive a sleep study, percent time below designated O2 saturation thresholds (<96%, <93%, and < 90%) will be calculated from both RHO and from the polysomnogram data. The number of desaturation events (defined as saturation drops below 90% for >10 seconds and > 20 seconds) will also be analyzed.

Duration of HOT was chosen as a primary outcome since it is the primary driver of caregiver emotional and financial health for families of infants on HOT. This outcome was driven by input from families themselves, through a process of including important stakeholders in the protocol development process. The PedsQL was chosen as an additional primary outcome because it is validated, accurate scale in which scores correlate with maternal psychiatric symptoms, poor child health, poor child adjustment, and increased child hospitalizations.

This protocol focuses on patient-centered outcomes that may demonstrate non-inferiority from a medical safety perspective, but may improve quality of life. While families place a priority on treatment strategies that optimize health, when there are multiple choices without a clear medically superior choice, then the impact of specific treatment choices on quality of life will help drive decision-making.

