**Table 1.**  
**O2 WEANING PARAMETERS**

	STANDARD OXYGEN MANAGEMENT ARM	CpOx OXYGEN MANAGEMENT ARM
CRITERIA FOR INCREASING O2 FLOW RATE	INABILITY TO MAINTAIN O2 SAT >93% AT PATIENT'S CURRENT O2 LEVEL FOR 20 MINUTES IN CLINIC VISIT CHALLENGE	INABILITY TO MAINTAIN O2 SAT >93% FOR >95% OF RECORDED TIME
CRITERIA FOR MAINTAINING CURRENT O2 FLOW RATE	ABILITY TO MAINTAIN O2 SAT >93% AT PATIENT'S CURRENT O2 BUT UNABLE TO MAINTAIN O2 SAT >93% AT WEANED FLOW RATE FOR 20 MINUTES IN CLINIC VISIT CHALLENGE	ABILITY TO MAINTAIN O2 SAT >93% FOR >=95% OF RECORDED TIME BUT UNABLE TO MAINTAIN O2 SAT >96% FOR >=95% OF RECORDED TIME
CRITERIA FOR WEANING O2 FLOW RATE	ABILITY TO MAINTAIN O2 SAT >96% AT WEANED FLOW RATE FOR 20 MINUTES IN CLINIC VISIT CHALLENGE	ABILITY TO MAINTAIN O2 SAT > 96% FOR >=95% OF RECORDED TIME

\* Clinic pass and fail will be determined per clinic assessment of oximeter alarms.

\*\* CpOx pass and fail will be determined by assessment of recorded oximetry. A minimum of 4 days of data, with a minimum of 8 hours per day, will be required for analysis to make any wean.

For infants in both arms, O2 weaning will proceed, when allowable per weaning criteria in the protocol, in 50% increments to a minimum of 125 cc/min. (For example, flow rate of 500 cc/min will be decreased to 250 cc/min, and 250 cc/min will be decreased to 125 cc/min.) Once infants achieve flow rates of 125 cc/min (or if they are discharged home from NICU on <125 cc/min), the next weaning step will be to room air during the day and nocturnal O2 only at a flow rate of 125 cc/min.

When infants in arm A have weaned to the final stage before discontinuation (O2 flow rate <= 125 cc/min, utilized only at night), they will be scheduled for an overnight polysomnography (PSG). These infants will have overnight recording with the Masimo Rad-8 pulse oximeter and serial data recorder on the nights prior to and during the PSG. Final decision regarding safe discontinuation of supplemental O2 therapy will be based on O2 saturation and growth outcomes; infants who do not meet criteria on the first PSG will remain on overnight O2 supplementation and repeat the PSG monthly until they pass.

To determine “Pass” of PSG or to determine ability to wean versus hold on current therapy versus escalate support, strict protocols to analyze O2 saturation status will be followed:

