**For patients randomized to HRO-based weaning:**

We will determine the number of seconds/hour with saturation >96, < 93, and < 90%, and the percentage of time below these thresholds for each recording interval (minimum 4-day epochs during weaning for

randomized infants, and 12 hour epochs for all infants both on the night before and during PSG) using target saturation limits defined in Table 1 to determine whether weaning can proceed.

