**For PSG evaluations:**

Infants will “pass” the PSG when they can maintain O2 saturation >93% for >95% of the time, with a minimum of 8 hours of nocturnal recording.

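### Secondary measure (c) compares recorded home oximetry with polysomnography without a common averaging time, a common time window or a per-hour event rate

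*Combined protocol and SAP*

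**What the plan says.** Section 4.e, secondary measure (c), applies to infants who have a sleep study. It computes percent time under three saturation thresholds (96, 93 and 90%) from both RHO and PSG, and adds a count: "The number of desaturation events (defined as saturation drops below 90% for >10 seconds and > 20 seconds) will also be analyzed". The Abstract gives the purpose of RHO in Arm A: "RHO will only be utilized on the night prior to and during the polysomnogram to compare these two modalities". The text after Table 1 has these infants undergo "overnight recording with the Masimo Rad-8 pulse oximeter and serial data recorder on the nights prior to and during the PSG", so the study oximeter also runs alongside the PSG.

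For RHO the settings are explicit. Under Home Pulse Oximeter Recording Procedures: "The oximeter will be set for the minimum (2 sec) averaging time". Under the heading on RHO-based weaning, the metrics are "number of seconds/hour with saturation >96, < 93, and < 90%, and the percentage of time below these thresholds for each recording interval", with "12 hour epochs for all infants both on the night before and during PSG".

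For PSG much less is fixed. The pass rule (For PSG evaluations) applies "with a minimum of 8 hours of nocturnal recording". The Arm A data section says "Polysomnogram data for infants in Arm A will also be extracted into data collection forms after completion of the polysomnogram". No PSG oximeter model, averaging time or sampling rate is given, although the study has nine centers.

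Section 5c names a GEE gamma regression for the comparison. It mentions no offset for recording time, does not say which RHO night is paired with the PSG, and does not say whether the two traces are cut to a common interval.

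**The concern.** Time under a threshold and the number of dips longer than 10 or 20 s depend on how the oximeter smooths the signal. A raw count also depends on how long the recording runs. If the two traces differ in either respect, part of any difference between RHO and PSG belongs to the settings. A real difference could equally be masked. The overall objective includes removing the need for PSG, so readers will take measure (c) as evidence on whether RHO can stand in for it. Recording both devices on the same night removes night-to-night variation. It does not remove a difference in averaging or in hours analysed.

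**Working it through.** The plan gives no sample size, margin or expected value for this comparison, so there is no figure to reproduce. Two checks apply.

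**1. Recording length.** Inputs: the 12-hour RHO epoch and the 8-hour PSG minimum. With an identical rate of r events per hour, the counts are 12r and 8r, so the ratio is 12r / 8r = 1.5. This is the upper end, reached only if the PSG stops at its minimum and RHO fills its epoch. If both run 12 hours the ratio is 1. Percent time and seconds per hour have the length divided out and carry no such factor. The event count in section 4.e has no stated denominator.

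**2. Averaging time.** The PSG setting is unknown, so 2 to 16 s is an assumed range.

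*Single square dip.* Take baseline B, lowest value N, length D, threshold T and a moving average of W seconds. The averaged trace is under T when more than a fraction p = (B − T)/(B − N) of the window lies in the dip. Time under T is then D + W(1 − 2p), or zero if the dip never fills that fraction.

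For B = 97, N = 88, T = 90, D = 12: p = 7/9.
- W = 2 s: 12 − 2(5/9) = 10.9 s, counted as a >10 s event.
- W = 4 s: 12 − 4(5/9) = 9.8 s, not counted.
- W = 8 s: 12 − 8(5/9) = 7.6 s, not counted.
- W = 16 s: the dip fills at most 12/16 = 0.75 of the window, below 7/9 = 0.78, so 0 s.

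The formula also shows the direction. Time under T rises with W when p < 1/2 and falls when p > 1/2. With B = 97:
- T = 96: p = 1/(97 − N), so time rises for any dip below 95%.
- T = 93: p = 4/(97 − N), so time rises if N < 89 and falls if N > 89. There is no stable sign.
- T = 90: p = 7/(97 − N), so time falls if N > 83 and rises for deeper dips.

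*Simulated nights.* Assumptions, none from the documents: baseline 97%, 10 triangular dips per hour, median length 18 s, lowest value 78 to 92%, 200 nights of 8 hours. The same true signal was averaged over different windows:

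| Averaging | % time <96 | % time <93 | % time <90 | events >10 s per 8 h | events >20 s per 8 h |
|---|---|---|---|---|---|
| 2 s | 4.65 | 3.28 | 1.98 | 19.5 | 2.8 |
| 4 s | 4.81 | 3.29 | 1.96 | 19.5 | 2.8 |
| 8 s | 5.35 | 3.36 | 1.84 | 19.8 | 2.9 |
| 16 s | 6.69 | 3.39 | 1.37 | 19.4 | 3.1 |

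Ratios to 2 s:
- Time under 96%: 4.81/4.65 = 1.03 at 4 s, 5.35/4.65 = 1.15 at 8 s, 6.69/4.65 = 1.44 at 16 s.
- Time under 90%: 1.96/1.98 = 0.99 at 4 s, 1.84/1.98 = 0.93 at 8 s, 1.37/1.98 = 0.69 at 16 s.
- Time under 93%: 3.39/3.28 = 1.03 even at 16 s.

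Total event counts move little, because some dips drop out while others merge or lengthen. In this set-up averaging mainly affects percent time, and recording length mainly affects counts.

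**The case against.** A reader might infer that the plan sets a 12-hour home trace against an 8-hour PSG. The documents do not say so. The 12-hour epoch is stated for both nights, and 8 hours is a minimum for passing the PSG, not the comparison window. The factor 1.5 is therefore a possibility that the plan leaves open, and it applies to the raw count only. What stands is that nothing makes the PSG trace run 12 hours or trims the two traces to their overlap.

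A reader might also infer that the PSG values are copied from reports and cannot be re-scored. The Arm A section mentions only extraction into forms, and section 4.e speaks of calculating from the PSG data. Laboratories may hold the saturation signal, which would make the fix easier.

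The simultaneous study oximeter is a real strength. It gives a same-night pair, and a home-to-laboratory pair on one device at one setting, so night effects can be separated from device effects. It does not equalise the averaging of two different oximeters.

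Finally, the averaging effect rests on assumed dip shapes and an assumed PSG setting. It is small at 2 to 4 s in the simulation, and nothing in the documents shows that laboratories use longer windows. That objection stands as to size. On its own, the unstated PSG setting would be no more than a missing detail.

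**Conclusion.** The point holds for secondary measure (c). As written, the plan allows a comparison over different hours and at different averaging times, with events left as a raw count. The length effect is at most a factor of 1.5 on event counts, assuming a PSG of exactly 8 hours against a full 12-hour RHO epoch; percent time and seconds per hour carry no built-in length bias. The averaging effect is illustrative. If a PSG oximeter averages over 8 to 16 s and dips resemble those simulated, time under 90% falls by 7 to 31% and time under 96% rises by 15 to 44% for the same signal. At 4 s the changes are 3% or less, and for time under 93% even the sign depends on dip depth. Because thresholds can move in opposite directions, no single correction factor would repair this afterwards.

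It would go too far to conclude that the RHO–PSG comparison is invalid or that the trial's main results are affected. Measure (c) enters neither duration of home oxygen nor parent quality of life.

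**What to change.** Add to section 5c, before the comparison is analysed:

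1. The main comparison is between the PSG and the study oximeter worn during that same PSG.
2. Both traces are scored by the same rules over the same clock interval, namely their overlap.
3. Desaturation events are reported per hour, or the model carries a log-hours offset.
4. Each laboratory's PSG averaging time is recorded, and the 2 s RHO trace is re-averaged to match it.
5. The night-before recording is a separate, secondary comparison.

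The cost is one added form field per PSG, use of the PSG saturation file where the laboratory holds it, and some extra analysis. Where no file is held, the recorded averaging time and the PSG start and stop times still allow the RHO trace to be matched approximately. The pass rule, the weaning criteria and the visit schedule are untouched.
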